## **15 DATA COLLECTION, RETENTION AND MONITORING**

### **15.1 Data Collection Instruments**

All clinical data will be entered by the Investigator in REDCap, a secure web-based data management system provided by the Clinical Translational Science Institute at UCLA that only the research team has access to. Each subject will also have a protocol-specific Case Report Form (eCRF) where the investigator will report the following information:

- Date of randomization
- Randomization to ARM 1 (standard dosing) or ARM 2 (gestational-age based dosing)
- Dosing of unfractionated heparin received
- Number of times unfractionated heparin dose was changed
- Side effects
- Adverse events

Subjects will not be identified by name in the study database or on any study documents to be collected by the Sponsor (or designee), but will be identified by a subject number and initials. If a correction is made on a CRF, the investigator will line through the incorrect data, write in the correct data and initial and date the change.

The investigator is responsible for all information collected on subjects enrolled in this study. All data collected during the course of this must be reviewed and verified for completeness and accuracy by the investigator.

### **15.2 Data Management Procedures**

The data will be entered in REDCap, a secure web-based data management system provided by the Clinical Translational Science Institute at UCLA. Only the research team will have access to the data and be responsible for data processing, in accordance with procedural documentations. All procedures for the handling and analysis of data will be conducted using good computing practices meeting FDA guidelines for the handling and analysis of data for clinical trials.

### **15.3 Archival of Data**

The database is safeguarded against unauthorized access by established security procedures; appropriate backup copies of the database and related software files will be maintained. Databases are backed up by the database administrator in conjunction with any updates or changes to the database.

#### **15.4 Availability and Retention of Investigational Records**

The Investigator must make study data accessible to the monitor, other authorized representatives of the Sponsor (or designee), IRB/IEC, and Regulatory Agency (e.g., FDA) inspectors upon request. A file for each subject must be maintained that includes the signed Informed Consent, HIPAA Authorization and Assent Form and copies of all source documentation related to that subject. The Investigator must ensure the reliability and availability of source documents from which the information on the CRF was derived.

All study documents (patient files, signed informed consent forms, copies of CRFs, Study File Notebook, etc.) must be kept secured for a period of two years following marketing of the investigational product or for two years after centers have been notified that the IND has been discontinued. There may be other circumstances for which the Sponsor is required to maintain study records and, therefore, the Sponsor should be contacted prior to removing study records for any reason.

#### **15.5 Monitoring**

Monitoring visits will be conducted by representatives of the Sponsor according to the U.S. CFR Title 21 Parts 50, 56, and 312 and ICH Guidelines for GCP (E6). By signing this protocol, the Investigator grants permission to the Sponsor (or designee), and appropriate regulatory authorities to conduct on-site monitoring and/or auditing of all appropriate study documentation.

#### **15.6 Subject Confidentiality**

In order to maintain subject confidentiality, only a subject number will identify all study subjects on CRFs and other documentation. Additional subject confidentiality issues (if applicable) are covered in the Clinical Study Agreement.

### **16 DATA AND SAFETY MONITORING PLAN**

SEE APPENDIX 3

### **17 ADMINISTRATIVE, ETHICAL, REGULATORY CONSIDERATIONS**

The study will be conducted according to the Declaration of Helsinki, Protection of Human Volunteers (21 CFR 50), Institutional Review Boards (21 CFR 56), and Obligations of Clinical Investigators (21 CFR 312).

To maintain confidentiality, all laboratory specimens, evaluation forms, reports and other records will be identified by a coded number and initials only. All study records will be kept in a locked file cabinet and code sheets linking a patient's name to a patient identification number will be stored separately in another locked file cabinet. Clinical information will not be released without written permission of the subject, except as necessary for monitoring by the FDA. The Investigator must also comply with all applicable privacy regulations (e.g., Health Insurance Portability and Accountability Act of 1996, EU Data Protection Directive 95/46/EC).

#### **17.1 Protocol Amendments**

Any amendment to the protocol will be written by the principal investigators. Protocol amendments cannot be implemented without prior written IRB/IEC approval except as necessary to eliminate immediate safety hazards to patients. A protocol amendment intended to eliminate

an apparent immediate hazard to patients may be implemented immediately, provided the IRBs are notified within five working days.

## **17.2 Institutional Review Boards and Independent Ethics Committees**

The protocol and consent form will be reviewed and approved by the IRB/IEC of each participating center prior to study initiation. Serious adverse experiences regardless of causality will be reported to the IRB/IEC in accordance with the standard operating procedures and policies of the IRB/IEC, and the Investigator will keep the IRB/IEC informed as to the progress of the study. The Investigator will obtain assurance of IRB/IEC compliance with regulations.

Any documents that the IRB/IEC may need to fulfill its responsibilities (such as protocol, protocol amendments, Investigator's Brochure, consent forms, information concerning patient recruitment, payment or compensation procedures, or other pertinent information) will be submitted to the IRB/IEC. The IRB/IECs written unconditional approval of the study protocol and the informed consent form will be in the possession of the Investigator before the study is initiated. This approval must refer to the study by exact protocol title and number and should identify the documents reviewed and the date of review.

Protocol and/or informed consent modifications or changes may not be initiated without prior written IRB/IEC approval except when necessary to eliminate immediate hazards to the patients or when the change(s) involves only logistical or administrative aspects of the study. Such modifications will be submitted to the IRB/IEC and written verification that the modification was submitted and subsequently approved should be obtained.

The IRB/IEC must be informed of revisions to other documents originally submitted for review; serious and/or unexpected adverse experiences occurring during the study in accordance with the standard operating procedures and policies of the IRB; new information that may affect adversely the safety of the patients of the conduct of the study; an annual update and/or request for re-approval; and when the study has been completed.

## **17.3 Informed Consent Form**

Informed consent will be obtained in accordance with the Declaration of Helsinki, ICH GCP, US Code of Federal Regulations for Protection of Human Subjects (21 CFR 50.25[a,b], CFR 50.27, and CFR Part 56, Subpart A), the Health Insurance Portability and Accountability Act (HIPAA, if applicable), and local regulations.

The Investigator will prepare the informed consent form, assent and HIPAA authorization and provide the documents to the Sponsor or designee for approval prior to submission to the IRB/IEC. The consent form generated by the Investigator must be acceptable to the Sponsor and be approved by the IRB/IEC. The written consent document will embody the elements of informed consent as described in the International Conference on Harmonisation and will also comply with local regulations. The Investigator will send an IRB/IEC-approved copy of the Informed Consent Form to the Sponsor (or designee) for the study file.

A properly executed, written, informed consent will be obtained from each subject prior to entering the subject into the trial. Information should be given in both oral and written form and subjects (or their legal representatives) must be given ample opportunity to inquire about details of the study. If appropriate and required by the local IRB/IEC, assent from the subject will also be obtained. If a subject is unable to sign the informed consent form (ICF) and the HIPAA

authorization, a legal representative may sign for the subject. A copy of the signed consent form (and assent) will be given to the subject or legal representative of the subject and the original will be maintained with the subject's records.

#### **17.4 Publications**

The preparation and submittal for publication of manuscripts containing the study results shall be in accordance with a process determined by mutual written agreement among the study Sponsor and participating institutions. The publication or presentation of any study results shall comply with all applicable privacy laws, including, but not limited to, the Health Insurance Portability and Accountability Act of 1996.

#### **17.5 Investigator Responsibilities**

By signing the Agreement of Investigator form, the Investigator agrees to:

1. Conduct the study in accordance with the protocol and only make changes after notifying the Sponsor (or designee), except when to protect the safety, rights or welfare of subjects.
2. Personally conduct or supervise the study (or investigation).
3. Ensure that the requirements relating to obtaining informed consent and IRB review and approval meet federal guidelines, as stated in § 21 CFR, parts 50 and 56.
4. Report to the Sponsor or designee any AEs that occur in the course of the study, in accordance with §21 CFR 312.64.
5. Ensure that all associates, colleagues and employees assisting in the conduct of the study are informed about their obligations in meeting the above commitments.
6. Maintain adequate and accurate records in accordance with §21 CFR 312.62 and to make those records available for inspection with the Sponsor (or designee).
7. Ensure that an IRB that complies with the requirements of §21 CFR part 56 will be responsible for initial and continuing review and approval of the clinical study.
8. Promptly report to the IRB and the Sponsor (or designee) all changes in the research activity and all unanticipated problems involving risks to subjects or others (to include amendments and IND safety reports).
9. Seek IRB approval before any changes are made in the research study, except when necessary to eliminate hazards to the patients/subjects.
10. Comply with all other requirements regarding the obligations of clinical investigators and all other pertinent requirements listed in § 21 CFR part 312.

[figure not shown]

## APPENDIX 1. Study Dosing Protocol

### Antepartum HEPARIN Dosing RCT Protocol

## APPENDIX 2. Schedule of Events

### ARM 1: Standard dose of unfractionated heparin

	VISIT (Day 1 – Baseline)	VISIT 2 (Day 2)	VISIT 3 (Day 3)	VISIT 4 (Day 6)	WEEKLY VISITS (Day 13, 20, 27+ until delivery or discharge)
Informed Consent	X				
Medical History	X				
Complete Physical Exam	X				
Abbreviated Physical Exam		X	X	X	X
Height	X				
Weight	X				
Demographics	X				
Medical/surgical history	X				
Concomitant medications	X				
Randomization	X				
Unfractionated heparin given	X	X	X	X	X
CBC	X			X	X
Trough aPTT	X	X 6 hours after heparin at ~15:00 PM	X 6 hours after heparin at ~15:00 PM	X 6 hours after heparin at ~15:00 PM	X 6 hours after heparin at ~15:00 PM
Trough Anti-Xa	X	X 6 hours after heparin at ~15:00 PM	X 6 hours after heparin at ~15:00 PM	X 6 hours after heparin at ~15:00 PM	X 6 hours after heparin at ~15:00 PM
Serum creatinine	X				
Peak aPTT			X 2 hours after heparin at ~11:00 AM		
Peak Anti-Xa			X 2 hours after heparin at ~11:00 AM		
Adverse Experiences		X	X	X	X
Follow-up trough aPTT (adjust or keep dose per APPENDIX 1)		X	X	X	X
Assess side effects				X	X

ARM 2 : Gestational-age based dose of unfractionated heparin

	VISIT (Day 1 – Baseline)	VISIT 2 (Day 2)	VISIT 3 (Day 3)	VISIT 4 (Day 6)	WEEKLY VISITS (Day 13, 20, 27+ until delivery or discharge)
Informed Consent	X				
Medical History	X				
Complete Physical Exam	X				
Abbreviated Physical Exam		X	X	X	X
Height	X				
Weight	X				
Demographics	X				
Medical/surgical history	X				
Concomitant medications	X				
Randomization	X				
Unfractionated heparin given	X	X	X	X	X
CBC	X			X	X
Trough aPTT	X	X 6 hours after heparin at ~15:00 PM	X 6 hours after heparin at ~15:00 PM	X 6 hours after heparin at ~15:00 PM	X 6 hours after heparin at ~15:00 PM
Trough Anti-Xa	X	X 6 hours after heparin at ~15:00 PM	X 6 hours after heparin at ~15:00 PM	X 6 hours after heparin at ~15:00 PM	X 6 hours after heparin at ~15:00 PM
Serum creatinine	X				
Peak aPTT			X 2 hours after heparin at ~11:00 AM		
Peak Anti-Xa			X 2 hours after heparin at ~11:00 AM		
Adverse Experiences		X	X	X	X
Follow-up trough aPTT (adjust or keep dose per APPENDIX 1)		X	X	X	X
Assess side effects				X	X

## **APPENDIX 3. Data and Safety Monitoring Plan**

Study Title: Randomized Control Trial of Unfractionated Heparin Dosing for Thromboprophylaxis of Hospitalized Antepartum Patients

Principal Investigator: [name] and [name]

### **I. Study Overview**

#### **A. Purpose of the study**

Venous thromboembolism (VTE) is one of the leading causes of maternal morbidity and mortality, and antepartum hospitalizations place pregnant patients at an even higher risk of developing thromboembolism. As a result, there is an increased emphasis on administering pharmacologic thromboprophylaxis for antepartum patients with prolonged hospitalizations.

Previously, standard dosing of unfractionated heparin was widely adopted for thromboprophylaxis in the pregnant population. However, due to a suspected altered metabolism of unfractionated heparin in pregnancy resulting in a decrease response, the American College of Obstetricians and Gynecologists (ACOG) and National Partnership for Maternal Safety (NPMS) currently recommends considering gestational age based dosing for unfractionated heparin for thromboprophylaxis in pregnancy with standard dosing as an alternative option. The data supporting altered dosing is very limited. In addition, increased dosing of heparin may result in challenges in anesthetic management, potentially limiting the receipt of neuraxial anesthesia resulting in increased need for general anesthesia associated with both increased maternal and fetal risks. The potential effects of higher prophylactic unfractionated heparin dosing in pregnant patients need to be further explored before being widely adopted for inpatient antepartum thromboprophylaxis. We propose this study to provide a direct comparison of gestational age based unfractionated heparin dosing to standard dosing of unfractionated heparin for pharmacologic thromboprophylaxis of hospitalized antepartum patients.

#### **B. Adherence statement**

The Data and Safety Monitoring Plan (SMP) outlined below will adhere to the protocol approved by the University of California, Los Angeles IRB.

### **II. Adverse events**

#### **A. Adverse event assessment**

The risks that may occur as part of participation in this study are detailed in section 2.1 of the study protocol. They include side effects from unfractionated heparin, discomfort of blood draws, and limitations in receipt of neuraxial anesthesia if resulting activated partial thromboplastin time (aPTT) is above the normal range. In order to mitigate risks to subject participants, the study protocol closely monitors lab values (aPTT and CBC) and provides subsequent decreases in dosing of unfractionated heparin. Because this study only includes hospitalized patients, subjects will be continuously assessed for side effects of unfractionated

heparin and adverse events by the medical team caring for her during the hospitalization. In addition, a formal assessment of side effects and adverse events will be performed by the investigator on weekly, while the subject is enrolled in the study.

**B. Adverse event reporting**

Every adverse event that is reported to the principal investigator or research team by the subject or medical staff caring for the subject and meets criteria will be documented. An adverse event report will be generated for each event and the report will include a description of the event, when it was reported, by whom it was reported, along with any official chart records or documentation to corroborate the event. The report will be provided to the IRB.

**III. Safety Review Plan and Monitoring**

**A. Justification of sample size**

Based on an informal/pilot review of antepartum admissions at our institution receiving gestational age-based dosing of unfractionated heparin, 40% of patients and an elevated aPTT value. Assuming 40% of patients receiving gestational age-based dosing and 3% receiving standard dosing had elevated serum aPTT values, a sample size of 18 women in each dosing group would have 80% power (alpha = 0.05) to demonstrate a significant difference in our primary outcome of evaluating the proportion of women with elevated aPTT values after heparin administration. We increased the sample size by 25% to account for post-randomization drop-out or lab sampling errors. We plan to recruit 46 patients with 23 patients in each arm.

**B. Safety and study progress reviews**

Study progress and safety will be reviewed monthly and more frequently if needed by the principle investigator. Review of subject accrual and compliance with inclusion/exclusion criteria will be performed to ensure that there are sufficient number of participants being enrolled and that they meet eligibility criteria. Adherence to treatment protocol and subject retention will be reviewed. Adverse events and side effects will also be reviewed by the principal investigator and reported per above. An interim analysis will be performed when 50% of the target sample size (23 subjects) have completed the study. A report will then be provided and contain a list and summary of adverse events, summary of recruitment and retention and reason for dropouts, and whether or not the study is on track to be completed and accomplish the stated aims.

**C. Stopping rules**

This study will be stopped prior to its completion if:

1. Gestational age-based dosing is associated with a significantly higher rate (defined as 50% of the study arm) of administration of general anesthesia despite dosing adjustments based on aPTT levels.
2. National guidelines from ACOG change during the trial and state that gestational age-based dosing should not be given for our study population.

3. Maternal or neonatal death occur secondarily to administration of unfractionated heparin.

**IV. Informed Consent**

Informed consent will be obtained from each subject before enrollment and per local institutional review board guidelines. Consent will be obtained in an ethical manner. The process of consenting will be obtained in the subject's primary language. Subjects will be provided with written material and will be given ample time to review the material and ask questions.

**V. Data Quality and Management**

Data on treatment protocol and lab values will be evaluated at least weekly by the research team and entered into the REDCap database, which is a secure web-based data management system provided by the Clinical Translational Science Institute at UCLA. The principal investigator will review all data collection forms for data completeness and accuracy. The collected data will be verified based on original source documents available in the electronic medical records. Only the research team will have access to the database.

**VI. Confidentiality**

All precautionary measures will be taken to ensure that confidentiality and privacy is maintained. All conversations with subjects and consents will be performed in a private setting. All data will be stored securely and only accessible to the research staff. Only a subject ID number will be associated with data to maintain subject confidentiality. A code sheet linking subject information to subject ID will be maintained but kept on a password protected computer and in a password protected file; this will only be accessible to the principle investigators.

Title of Study: Heparin Prophylaxis Dosing for Antepartum Hospitalizations (HEPDOSE)

NCT Number: NCT04635839

Document Date: June 27, 2022

Document: Statistical Analysis Plan

Traditional univariate analysis was performed for our primary and secondary outcomes with Chi-square or Fisher exact test for categorical variable and t-test or Wilcoxon rank-sum test for continuous variables. A logistic regression analysis was performed to further assess the association of elevated aPTT with gestational age-based dosing of unfractionated heparin relative to standard dosing. We also performed a multivariate logistic regression to adjust for confounders. Confounders included in the model were a priori covariates that potentially could affect the response to unfractionated heparin along with baseline characteristics from our univariate analyses comparing study arm groups that had a p value < 0.2. Via a stepwise regression, none of the variable demonstrated a significant effect on our primary outcome. However, for our final model we elected to adjust for creatinine and obesity based on clinical relevance and a priori knowledge of these factors being potential confounders that may not have been detected in our study cohort due to the small sample size.

Statistical significance was defined as a p-value of < 0.05 or non-overlapping 95% confidence intervals (CI). All analyses were conducted using Statistical Analysis Software (SAS), version 9.4 (Copyright 2013, SAS Institute, Inc. Cary, NC).

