STATISTICS Primary Analysis Plan	
Analysis of the primary endpoint of whether or not there was an elevation in aPTT in each dosing group will be performed with a Chi-squared test. Multivariate logistic regression analysis will be performed to determine which factors were associated with an elevated aPTT value. Comparison of maternal demographics, baseline characteristics, additional maternal outcomes, and neonatal outcomes between the two groups will be analyzed using Student's t-test for parametric data, Wilcoxon signed-rank test for nonparametric data, and Chi-squared or Fisher's exact test for comparison of proportions. Descriptive statistics will be performed to summarize which dose resulted in a normal aPTT value and anti-Xa within goal range. Statistical significance will be set at a p-value of < 0.05 or 95% confidence interval not overlapping.

Rationale for Number of Subjects	
Assuming 40% of patients receiving gestational age-based dosing and 3% receiving standard dosing have an elevated aPTT value, a sample size of 36 women (18 in each arm) would have 80% power to demonstrate a significant difference between the proportion of women with elevated aPTT values after administration. We plan to recruit 46 (23 in each arm) to account for post-randomization drop out and lab sampling errors.

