## **11 STATISTICAL METHODS AND CONSIDERATIONS**

Prior to the analysis of the final study data, a detailed Statistical Analysis Plan (SAP) will be written describing all analyses that will be performed. The SAP will contain any modifications to the analysis plan described below.

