### **11.1 Data Sets Analyzed**

All patients randomized into the study that received two doses of unfractionated heparin and had at least one aPTT measurement available for review will be included within the analysis.

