### **11.3 Analysis of Primary Endpoint**

Analysis of the primary endpoint of whether or not there was an elevation in aPTT in each dosing group will be performed with a Chi-squared test. Comparison will be considered statistically significant at a p-value of  $< 0.05$ .

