### **11.4 Analysis of Secondary Endpoints**

Comparison of maternal demographics, baseline characteristics, additional maternal outcomes, and neonatal outcomes between the two groups will be analyzed using Student's t-test for parametric data, Wilcoxon signed-rank test for nonparametric data, and Chi-squared or Fisher's exact test for comparison of proportions. Descriptive statistics will be performed to summarize which dose resulted in a normal aPTT value and anti-Xa within goal range. Multivariate logistic regression analysis will be performed to determine which factors were associated with an elevated aPTT value. Statistical significance will be set at a p-value of  $< 0.05$  or 95% confidence interval not overlapping.

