### **11.5 Sample Size and Randomization**

Based on an informal/pilot review of antepartum admissions at our institution receiving gestational age-based dosing of unfractionated heparin, 40% of patients and an elevated aPTT

value. Assuming 40% of patients receiving gestational age-based dosing and 3% receiving standard dosing had elevated serum aPTT values, a sample size of 18 women in each dosing group would have 80% power (alpha = 0.05) to demonstrate a significant difference in our primary outcome of evaluating the proportion of women with elevated aPTT values after heparin administration. We increased the sample size by 25% to account for post-randomization drop-out or lab sampling errors. We plan to recruit 46 patients.

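### Does the SAP's choice of chi-square or Fisher's exact test leave the primary comparison open in a way that needs correcting?

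*SAP*

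**What the plan says.** Protocol 11.3 gives the primary analysis one test: "there was an elevation in aPTT in each dosing group will be performed with a Chi-squared test", with significance at p < 0.05. The synopsis says the same. Protocol 11.4 offers "Chi-squared or Fisher's exact test for comparison of proportions" for demographics, baseline characteristics, and other maternal and neonatal outcomes.

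The SAP, dated June 2022 and written in the past tense, merges the two: "Traditional univariate analysis was performed for our primary and secondary outcomes with Chi-square or Fisher exact test for categorical variable".

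Protocol section 11 says how changes are to be recorded: "The SAP will contain any modifications to the analysis plan described below". The SAP labels nothing as a change to the primary test.

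Protocol 11.5 gives the design basis, "a sample size of 18 women in each dosing group would have 80% power (alpha = 0.05", for 40% against 3%, raised to 46 women in all (23 per arm). Protocol 11.1 limits the analysis to randomised women who "received two doses of unfractionated heparin and had at least one aPTT measurement available for review", so the analysed arms may be smaller and unequal.

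**The concern.** The protocol fixes one test for the primary endpoint and the SAP appears to allow two, with no selection rule. In a large trial this would be harmless. Here the expected number of elevated values per arm is about 4 to 5, where the Pearson chi-square and Fisher's exact test often fall on opposite sides of 0.05. An analyst who had seen the data could in principle pick the test that gave the preferred answer, and a reader of these two documents cannot tell which p-value decides the primary conclusion. The stated power might also belong to one test and not the other. If these worries held, both the type I error and the design power of the primary comparison would be in doubt.

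**Working it through.** **Inputs.** Rates 0.40 and 0.03, 18 per arm, 80% power and alpha 0.05 (protocol 11.5); 23 per arm recruited (synopsis, Appendix 3). Sidedness is not stated; two-sided is assumed unless noted.

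**1. The plan's own figure.** The pooled normal formula without continuity correction is

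n = [z(0.975)·√(2·p̄·(1−p̄)) + z(0.80)·√(p1(1−p1) + p2(1−p2))]² / (p1−p2)²

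with p̄ = 0.215:

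- z(0.975)·√(2·0.215·0.785) = 1.1387
- z(0.80)·√(0.24 + 0.0291) = 0.8416 × 0.5187 = 0.4366
- n = (1.1387 + 0.4366)² / 0.37² = 18.13

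Power at 18 per arm is Φ[(0.37·√18 − 1.1387)/0.5187] = 79.7%. The stated 18 and 80% are reproduced, apart from rounding 18.13 down.

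This does not tie the design to one test. A one-sided Fisher test has exact power 78.2% at 17 per arm and 81.9% at 18, so it would also lead to 18.

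**2. Exact power and disagreement.** All 2×2 tables were enumerated under Binomial(n, 0.40) and Binomial(n, 0.03), with each test taken at two-sided 0.05.

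| | 18 per arm | 23 per arm |
|---|---|---|
| Chi-square, uncorrected | 85.4% | 93.6% |
| Fisher if an expected count is below 5, otherwise chi-square | 76.6% | 90.5% |
| Fisher | 74.9% | 88.2% |
| Chi-square, continuity-corrected | 68.3% | 82.4% |
| Uncorrected chi-square and Fisher disagree | 10.5% | 5.5% |

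The mean expected count of elevated values per arm is n × 0.43/2: 3.87 at 18 and 4.95 at 23. An expected count below 5 arises in 79% and 45% of trials respectively, so Fisher is a natural candidate.

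**3. Direction of the disagreement.** Examples at 23 per arm:

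- 4 v 0: chi-square 0.036, Fisher 0.109
- 6 v 1: 0.040, 0.096
- 8 v 2: 0.032, 0.071

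Over all 36 pairs of arm sizes from 18 to 23, no table has Fisher significant and the uncorrected chi-square not. The continuity correction only makes the chi-square statistic smaller. So the tables in which any of the three tests rejects are exactly those in which the uncorrected chi-square rejects.

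**4. What free choice could do to type I error.** It follows that taking the smallest p-value has the size of the uncorrected chi-square and no more. At a common rate of 21.5% that is 4.7% at 18 per arm and 5.2% at 23. The maximum over common rates is 6.5% and 5.4%, reached at a rate of 50%. Fisher's maximum over the 36 pairs is 4.0%.

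**5. Unequal arms.** Over the 30 unequal pairs from 18 to 23, disagreement at the planning rates runs from 0.05% (21 gestational-age v 22 standard) to 12.1% (23 v 18), median 3.6%. The top value needs all five exclusions to fall in the standard arm; chi-square power is then 90.5% and Fisher 78.3%. One exclusion can move Fisher across the line: 6/23 v 1/23 gives 0.096, 6/22 v 1/23 gives 0.047.

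**The case for a change.** The strongest case for acting is that the primary conclusion should rest on one identified test. Protocol 11.3 supplies one and the SAP blurs it. Section 11 makes the SAP the place to record a change, and none is recorded. The choice is live, since a common reason for switching to Fisher would be met in 45% to 79% of trials at the planned sizes. Fisher falls below 80% power at 18 per arm. Stating the test would take one line.

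The wording difference and these figures stand. The consequence does not follow, for three reasons.

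- The SAP sentence is a summary of several outcomes. It does not say that Fisher decided the primary result. As it declares no change, 11.3 still governs the primary endpoint, with the either-test wording serving the rest as in 11.4.
- Neither test is wrong here. Chi-square has more power but can slightly exceed 5%; Fisher holds its level but loses 5 to 11 points of power. Experienced statisticians differ on this with expected counts near 5.
- The SAP already describes model results, whereas section 11 expects it before the final analysis. A selection rule written in now could not count as prespecified.

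The added significance clause ("Statistical significance was defined as a p-value of < 0.05 or non-overlapping 95% confidence intervals (CI", also in the synopsis as "0.05 or 95% confidence interval not overlapping") does not alter this. Protocol 11.3 uses the p-value alone. Requiring the two arm-wise intervals not to overlap is stricter than 5%, about 2·[1 − Φ(1.96·√2)] = 0.6% with equal standard errors.

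**Conclusion.** No change to the plan. The two documents differ in wording, but what is left open is a detail that an analyst fills sensibly: chi-square as 11.3 says, or Fisher when counts are small. At the planned 23 per arm the choice alters the verdict in 5.5% of trials, always with chi-square the significant test. It adds no type I error beyond that of the uncorrected chi-square, and power is above 80% whichever version is used. Nothing in the documents shows that Fisher was used for the primary endpoint or that the result turned on the choice; no primary counts are given. A results report would name the test beside its p-value as a matter of course, which does not require rewriting the SAP.

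This rests on two-sided testing, the planning rates of 40% and 3%, and analysed arms of 18 to 23. At the lower end, or with exclusions concentrated in the standard arm, disagreement rises to 10.5% to 12.1% and Fisher's power drops to 74.9% to 78.3%. The direction of disagreement stays the same.
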